3 STUDY DESIGN AND DESCRIPTION

3.1 Study design

This is a prospective, randomized, multicenter, controlled, open, parallel group phase III study.

After initiation of the study, patients will be screened consecutively and eligible patients will be enrolled into the study at each center. To achieve comparable intervention groups and to minimize a potential selection bias, patients will be allocated in a concealed fashion by means of randomization using a centralized web-based tool (www.randomizer.at).

Each sites' principal investigator has to declare to the coordinating investigator/sponsor that he/she will conduct the study according to the protocol, ethical rules, and to provide the support as needed. To minimize a potential performance bias, this will be fixed in a contract prior to commencing the study. The clinical monitor will introduce the sites in detail to study procedures and documentation in advance.

Bias by potential influential factors will be addressed by inclusion as covariates into the statistical analysis. Independent clinical on-site monitoring to ensure patients safety and integrity of the clinical data in adherence to study protocol will focus on source data documentation, correctness of data, and adherence to study procedures, e.g. randomization and treatment.

Based on the performed interventions and planned analysis blinding is not feasible to minimize a detection bias, because the interventions can easily be differentiated due to visible side effects such as obesity, which is only expected in the control group. Furthermore, MMF is used in liquid form and prednisone as a tablet. The primary endpoint is based on standardized diagnostic work-up results, i.e. is an objective criteria.

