5.4.2 Dosage Schedule

Maximum duration of treatment: 12 weeks after first day of initial treatment of SSNS. Patients will receive the whole medication for the complete intervention period.

Control intervention:

- The Prednisone, which is continued for a total of 6 weeks with the dosage of 60 mg/m² BSA/d (maximum 80 mg), is given once a day (quaque die (QD)), twice a day (bis in die (BID)) or three times daily (ter in die (TID)).
- The Prednisone, which is given for another total of 6 weeks with the dosage of 40 mg/m² BSA (maximum 60 mg) is given on alternate days (every other day) in one dose in the morning

Resorption of prednisone is independent of food intake.

Experimental intervention:

- Mycophenolate mofetil (MMF) is given in a dosage of 1200 mg/m² BSA/d as a suspension (200 mg/mL) until 12 weeks total treatment duration. MMF is given twice a day (bis in die (BID) = every 12 hours (± one hour).
- The suspension of MMF should be mixed in the study center (according to the Fachinformation).
- The persons having care and custody of the child are informed, that MMF should be given 30 minutes before or 60 minutes after food intake.
- For the first two weeks from randomization/visit1 on, prednisone is given with the dosage of 40 mg/m² BSA (maximum 60 mg) on alternate days (every other day) in one dose in the morning

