6 STUDY METHODS

6.1 Time Sequence and Frames

FLOW CHART/STUDY SCHEDULE

alternate day = every second day

All patients who seem suitable for study participation and take part in the screening, will receive a screening number. At the end of the screening phase the suitability of the patient is assessed finally.

Parents of children with initial episode of idiopathic nephrotic syndrome aged between 1 and 10 years and treated with standard regime will be informed about the ongoing INTENT study either by the study center or by their pediatrician who will inform the study center as well.

If the child with initial episode of idiopathic nephrotic syndrome is steroid-sensitive (remission within 28 days), the patient fulfills the inclusion criteria. The persons having care and custody of the child and the patient, if ≥6 years of age, will be informed about the INTENT study by the study center and give written assent/consent.

The maximum time period between remission (=screening) and visit 1 are 5 days.

[figure not shown]
Allocation to INTENT study in detail

Patient with a first episode of idiopathic nephrotic syndrome

Initiation of standard therapy for the first episode of idiopathic nephrotic syndrome in children = day 1

Remission after ≤ 4 weeks = steroid-sensitive nephrotic syndrome (SSNS)

[figure not shown]

(Day1: Start with standard therapy for first episode of idiopathic nephrotic syndrome in children)

Screening

In the screening, date of diagnosis of nephrotic syndrome, date of start with standard therapy for nephrotic syndrome, and date of remission is documented in the eCRF besides the proven inclusion and exclusion criteria. For checking the exclusion criteria concerning eGFR, leucocyte count and hemoglobin concentration the most recent lab values should be used; they should have been obtained no more than 28 days prior to visit 1. In addition, infections and vaccinations are documented that have taken place within two weeks prior to the diagnosis of nephrotic syndrome.

Scope and frequency of study visits

Time Sequence and frames

Visit	Visit no.	Time	Time window [days]
Screening/Start of study treatment	Visit 1		0-5 days after date of remission*
Interim visit	Visit 2	4 weeks after visit 1	± 5 days

Last week of treatment visit	Visit 3	11 weeks after day 1 (=first day of treatment with standard therapy)	± 7 days
First follow-up	Visit 4	6 months after day 1 (= first day of treatment with standard therapy)	± 14 days

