Second follow-up	Visit 5	9 months after day 1 (= first day of treatment with standard therapy)	± 14 days
Third follow-up	Visit 6	15 months after day 1 (= first day of treatment with standard therapy)	± 14 days
Fourth follow-up	Visit 7	21 months after day 1 (= first day of treatment with standard therapy)	± 14 days
End of study	Visit 8	27 months after day 1 (= first day of treatment with standard therapy)	± 14 days

^{*} In case the patient is randomized into the experimental intervention group at the fifth day after remission has been achieved start of mycophenolate mofetil is possible at the same day or the next day (i.e. day 6 after remission).

Visit 1

Visit 1 is scheduled at the point in time of allocation to the INTENT study and randomization (0-5 days after date of remission). The exact date depends on the time between first day of treatment with standard therapy for first episode of idiopathic nephrotic syndrome in children (= day 1) and the point in time of remission (this may vary between day 5 until day 28).

At visit 1 the history of the patient is documented: Age, gender, postal code (first 4 of 5 digits), known allergies, other chronic diseases, family history concerning kidney disease. Furthermore side effects of the previous standard treatment are retrieved in yes/no manner (Behavioral disturbances since diagnosis: child feels sad, anxious, irritable, as well as euphoric state, aggressive state, nausea, vomiting (defined as a frequency of more than 1 times per day), diarrhea (defined as a frequency of more than 4 loose stools daily), headache, muscle weakness, any new infection (e.g. respiratory tract infection, gastroenteritis, urinary tract infection)). Application of any current medication (other than immunosuppressive agents) is documented.

The physical examination contains investigation of the skin in yes/no manner (acne, cushingoid facies, striae, and hypertrichosis), further pathological organ-specific findings in yes/no/not done manner (lymphadenopathy, pharyngitis, otitis media, heart murmur, arrhythmia, respiratory tract infection, abdominal pain, and muscle weakness) and pubertal status.

Measurement of weight, height (BMI is computed) and blood pressure after 3 minutes rest are done and documented.

A sample of spot urine is analyzed with dip stick (Albustix®) and quantitatively for creatinine, protein, albumin in the laboratory of the study center (urine protein/creatinine ratio is computed).

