The blood test contains: blood cell count (leukocytes, erythrocytes, hemoglobin, and thrombocytes), HbA_{1c} , creatinine, blood urea/blood urea nitrogen (BUN), uric acid, calcium, phosphate, alkaline phosphatase, 25-OH Vitamin D, total protein, albumin, GPT/ALT, IgG, IgE, Cholesterol.

Study specific investigations are:

- 24 h ambulatory blood pressure measurement (24h-ABPM) performed by the study center with documentation of the median of systolic blood pressure (day), of the median of diastolic blood pressure (day), the median of systolic blood pressure (night), the median of diastolic blood pressure (night).
- o **Ophthalmologic investigation** performed by any ophthalmologist will document cataract (yes/no) and glaucoma (yes/no)
- O Health related quality of life (HRQoL) DISABKIDS as standardized questionnaires to assess health related quality of life is used. There exists a parental questionnaire, a questionnaire for children aged ≥8 years and one for children aged 4-7 years of age. Children below 4 years of age will not receive a questionnaire.
- Echocardiography (Echocardio.) is optional for the INTENT study and will be performed by a pediatric cardiologist. The documented parameters are: LVID (left ventricular internal diastolic diameter), LVIS (left ventricular internal systolic diameter), PWT (posterior wall thickness), and IVST (interventricular septic thickness). The LVID index, the LV FS (Left ventricular fractional shortening), LVM (left ventricular mass), LVM index, and LVH (Left ventricular hypertrophy) are computed.

These study specific investigations can be performed in a time frame of -21 days/ +7 days around the visit date.

The persons having care and custody of the child and the patient will be informed about the randomized medication, especially its handling, dosing, intake in relation to food intake and storage (see 5.4.2).

Further, the use of the patients´ diary is explained. Daily dip stick (Albustix®), given medication (if control intervention: dosage of prednisone in mg; if experimental intervention: dosage of MMF in ml and dosage of prednisone in mg), as well as days of missing school, infections, hospitalization, or other events the persons having care and custody of the child feel important to document.

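### The visit 1 window lets the only reference value for quality of life and ambulatory blood pressure be taken up to 7 days after open randomisation and start of study treatment

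*Protocol*

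**What the plan says.** Protocol section 6.1 places visit 1 at allocation: "Visit 1 is scheduled at the point in time of allocation to the INTENT study and randomization (0-5 days after date of remission"). The visit table in the same section labels it "Screening/Start of study treatment". A footnote for children randomised on the fifth day after remission adds that "start of mycophenolate mofetil is possible at the same day or the next day". In the experimental arm the prednisone regimen changes at the same point (section 5.4.2): "For the first two weeks from randomization/visit1 on, prednisone is given with the dosage of 40 mg/m² BSA (maximum 60 mg) on alternate days". The control arm stays on 60 mg/m² per day until six weeks from the start of therapy.

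The trial is not blinded (section 3.1): "This is a prospective, randomized, multicenter, controlled, open, parallel group phase III study". The visit 1 text in section 6.1 has the arm disclosed there: "The persons having care and custody of the child and the patient will be informed about the randomized medication".

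Under visit 1, section 6.1 lists four study-specific investigations: 24-hour ambulatory blood pressure, ophthalmology, DISABKIDS and optional echocardiography. For all four it states: "These study specific investigations can be performed in a time frame of -21 days/ +7 days around the visit date". They are repeated only at visits 5 and 8. Nothing in the protocol requires them before disclosure of the arm or before the first allocated dose.

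**The concern.** A reference value should be free of the allocated treatment and of knowledge of it. Here a site may comply fully with the protocol and still obtain the visit 1 value a week after both.

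Two mechanisms are possible. A parent or child who already knows the arm may answer a quality-of-life questionnaire differently, in either direction. An ambulatory blood pressure recorded after a further week of daily prednisone in one arm, and alternate-day prednisone plus mycophenolate in the other, may already differ by arm. If such values then served as baseline, a change score or baseline adjustment could remove part of a true difference or add a spurious one.

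Reduced steroid toxicity is the stated reason for the trial (section 1.2), and quality of life is a secondary endpoint (section 2.2). The window is a data-collection rule. A statistical analysis plan can set late values aside, but it cannot recover a measurement that was never taken before allocation.

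**Working it through.** The plan gives no figure of its own on this point, so there is none to reproduce. The check is date arithmetic and a sum of nominal prednisone doses.

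**Inputs (Protocol)**
- Window: 21 days before to 7 days after visit 1 (6.1).
- Remission: day 5 to day 28 of initial therapy; visit 1: 0 to 5 days after remission (6.1).
- Control prednisone: 60 mg/m² daily for 6 weeks in total, i.e. to day 42 (5.4.2).
- Mycophenolate arm: prednisone 40 mg/m² on alternate days for two weeks from visit 1 (5.4.2).

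**Position of the window**
- Visit 1 falls between day 5 and day 28 + 5 = 33.
- The late end falls between day 5 + 7 = 12 and day 33 + 7 = 40. Since 40 < 42, every control child is still in the daily phase at the late end.
- The window spans 21 + 7 = 28 days, of which 7/28 = 25% lie after randomisation.

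**Nominal prednisone in the 7 days from visit 1, before dose caps**
- Control: 7 × 60 = 420 mg/m².
- Mycophenolate arm: 3 or 4 alternate-day doses, 3 × 40 = 120 to 4 × 40 = 160 mg/m².
- Difference: 420 − 160 = 260 to 420 − 120 = 300 mg/m², plus about a week of mycophenolate (6 days if it starts the day after randomisation).

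**The same difference in cumulative terms**

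All children have been on 60 mg/m² per day since day 1. With visit 1 on day d, shared prior exposure is (d − 1) × 60.

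| Visit 1 on day | Prior, both arms | Control at +7 | Mycophenolate arm at +7 | Ratio |
|---|---|---|---|---|
| 7 | 360 | 780 | 480–520 | 1.5–1.6 |
| 14 | 780 | 1200 | 900–940 | about 1.3 |
| 33 | 1920 | 2340 | 2040–2080 | about 1.1 |

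The absolute gap is the same in every row. The ratio shrinks as shared exposure grows.

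**Which measures are vulnerable**
- DISABKIDS: reported by parent or child, with the arm known from visit 1. This is the main concern.
- Ambulatory blood pressure: an objective recording, but I assume it could respond within days to a different steroid exposure.
- Cataract and glaucoma (yes/no): cataract is unlikely to arise in 7 days, so the concern is small.
- Echocardiography: optional and not an endpoint in section 2.2, so the concern is small.
- Resting blood pressure is not among the investigations given the wider window.

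The protocol gives no effect sizes for these outcomes and no expected share of children measured late. The bias in any endpoint therefore cannot be computed.

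**The case against.** The protocol never calls these values a baseline and states no change-from-baseline analysis for them. Section 8.4 makes all secondary outcomes descriptive and leaves detail to the analysis plan, which is not at hand. That plan could define baseline as the last value before the first dose, and a comparison of arms at visits 5 and 8 needs no baseline. Section 2.2 names arterial hypertension, checked at all visits, but not ambulatory blood pressure. Section 2.2 also says the toxicity benefit is not tested confirmatorily. The +7 days plausibly exist because an ophthalmologist, a 24-hour recording and a cardiologist are hard to schedule. All of this stands, and it limits the consequence. It does not remove the point that the rule permits the only reference value to be collected after disclosure and first dose.

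A reader might infer more than the text supports:
- That exposure differs about threefold at the late end. This counts only prednisone after visit 1. Cumulatively the ratio is about 1.1 to 1.6 for visit 1 on days 7 to 33.
- That the early end of the window is also a bias. Section 6.1 says "The maximum time period between remission (=screening) and visit 1 are 5 days", so values from days −21 to −6 precede remission and some precede therapy. They also precede randomisation, so they cannot differ systematically by arm. At most they add noise, and a pre-steroid value may even be the better reference for steroid toxicity.
- That all 340 children are exposed on every measure. Echocardiography is optional, and children under 4 receive no questionnaire.

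**Conclusion.** The point holds as a limited weakness in data collection. The protocol allows the single reference value for DISABKIDS and ambulatory blood pressure to be taken up to 7 days after randomisation and start of study treatment in an open trial. By then the arms can differ by 260 to 300 mg/m² in nominal prednisone, on top of shared earlier exposure.

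This rests on two assumptions: that the visit 1 value will be used as a reference, which follows from the visit 1, 5 and 8 schedule rather than from a stated analysis, and that some children are in fact measured late.

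The documents do not support saying that the toxicity or quality-of-life comparison is biased by a known amount, or that the eye findings are compromised. The primary endpoint and the sample size (272 analysed, 340 randomised) are unaffected. The change is worth making because it is cheap and because a missed pre-allocation value cannot be recovered later.

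**What to change.** Amend the visit 1 window sentence in section 6.1 as follows.

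1. DISABKIDS is completed at visit 1 before the allocation is disclosed to the family.
2. 24-hour ambulatory blood pressure, eye examination and echocardiography keep the 21-day look-back and are done before the first allocated dose where feasible.
3. If one of these is done later, it stays in the eCRF with its date but is not used as a pre-treatment baseline. For ambulatory blood pressure, this exclusion should apply at least in a sensitivity analysis.

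The protocol already writes a look-back-only window for the eligibility laboratory values (no more than 28 days before visit 1), so the form is familiar to sites.

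The questionnaire change costs nothing. The rest costs a revised sentence and a date check in the eCRF. The real downside is some missing ambulatory blood pressure, eye or echocardiography baselines, because visit 1 is at most 5 days after remission and outside appointments may not fit. That is why the second item says where feasible and the early limit is left alone. No dose or clinical rule changes.

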7 ADVERSE EVENTS

7.1 Definitions

7.1.1 Adverse Event

According to GCP, an adverse event (AE) is defined as follows: Any untoward medical occurrence in a subject administered a pharmaceutical product and which does not necessarily have a causal relationship with this treatment. An AE can therefore be any unfavorable and unintended sign (including an abnormal laboratory finding), symptom, or disease temporally associated with the use of a medicinal (investigational) product, whether or not related to the medicinal (investigational) product.

An AE may be:

- New symptoms/medical conditions
- New diagnosis
- Changes of laboratory parameters
- Intercurrent diseases and accidents
- Worsening of medical conditions/diseases existing before clinical study start
- Increase of frequency or intensity of episodical diseases.

A pre-existing disease or symptom will not be considered an adverse event unless there will be an untoward change in its intensity, frequency or quality. This change will be documented by an investigator.

AEs are classified as "non-serious" or "serious".

7.1.2 Serious Adverse Event

A serious adverse event (SAE) is one that at any dose:

- Results in death
- Is life-threatening (the term life-threatening refers to an event in which the subject was at risk of death at the time of event and not to an event which hypothetically might have caused death if it was more severe)
- Requires hospitalization or prolongation of existing hospitalization
- Results in persistent or significant disability/incapacity
- Is a congenital anomaly/birth defect or
- Is otherwise medically relevant

Hospitalization for performing protocol-required procedures or administration of study treatment is not classified as an SAE. Hospitalizations for disease-related procedures (imaging, laboratory tests) or any procedures planned before entry into the study are not considered SAEs. Hospitalizations for social reasons in the absence of an adverse event are not classified as SAEs either.

Medical and scientific judgment should be exercised in deciding whether expedited reporting is appropriate in other situations - such as important medical events that may not be immediately life threatening or result in death or hospitalization but may jeopardize the patient or may require intervention to prevent one of the other outcomes listed above. These should also usually be considered serious (examples of such events are intensive treatment in an emergency room or at home for allergic bronchospasm; or convulsions that do not result in hospitalization).

7.1.3 Serious Adverse Reaction

SAEs that potentially may be attributed to the investigational medicinal product (IMP) are to be classified as Serious Adverse Reactions (SARs).

7.1.4 Expectedness

An 'unexpected' adverse reaction is one the nature or severity of which is not consistent with the applicable product information, e.g., Summary of Product Characteristics (SmPC). Furthermore, reports which add significant information on specificity or severity of a known adverse reaction constitute 'unexpected' events.

7.1.5 Suspected Unexpected Serious Adverse Reaction (SUSAR)

SAEs that are both 'suspected', i.e., possibly related to the study drug (investigational medicinal product (IMP)) and 'unexpected', i.e., the nature and/or severity of which is not consistent with the applicable product information are to be classified as Suspected Unexpected Serious Adverse Reactions (SUSARs).

In case, either the investigator who primary reported the SAE or the second assessor, classifies the SAE as 'suspected' [either as 'definitely' or 'probable' or 'possible' related to IMP or 'not assessable'] and the SAE is unexpected the event will be categorized as a SUSAR.

All SUSARs are subject to an expedited reporting to the responsible ethics committee(s), the competent authority and to all participating investigators.

7.1.6 Grading of AEs

The grading of AEs in this study will be carried out on the basis of the 5-grade scale defined in the CTCAE v4.3:

Grade 1: Mild

Grade 2: Moderate
Grade 3: Severe

Grade 4: Life-threatening or causing disablement

Grade 5: Death

The grading of all AEs listed in the CTCAE v4.3 will be based on the information contained therein. The grading of all other AEs, i.e., those which are not listed in the CTCAE v4.3 will be performed by a responsible investigator, based on definitions given above.

7.1.7 Relationship and Outcome of AEs

The investigator will evaluate each AE that occurred after administration of the IMP regarding the **relationship** with the administration of the IMP:

Definitely related: There is a reasonable possibility that the event may have been caused by

the IMP. A certain event has a strong temporal relationship and an

alternative cause is unlikely.

Probable: An AE that has a reasonable possibility that the event is likely to have

been caused by the IMP. The AE has a timely relationship and follows a known pattern of response, but a potential alternative cause may be

present.

Possible: An AE that has a reasonable possibility that the event may have been

caused by the IMP. The AE has a **timely relationship** to the IMP; **however, the pattern of response is untypical**, and an alternative cause seems more likely, or there is significant uncertainty about the cause of

the event.

Unlikely: Only a remote connection exists between the IMP and the reported

adverse event. Other conditions including concurrent illness, progression or expression of the disease state or reaction of the concomitant

medication appear to explain the reported adverse event.

Not related: An AE that does not follow a reasonable temporal sequence related to the

IMP and is likely to have been produced by the subject's clinical state,

other modes of therapy or other known etiology.

Not assessable: There is insufficient or incomplete evidence to make a clinical

judgment of the causal relationship.

All subjects who have reportable AEs, whether considered associated with the use of the study medication or not, must be monitored to determine the **outcome**. The clinical course of the AE will be followed up until resolution or normalization of changed laboratory parameters or until it has changed to a stable condition. This also holds for ongoing AEs/SAEs of withdrawn subjects.

The outcome of an AE at the time of the last observation will be classified as:

Recovered/resolved: All signs and symptoms of an AE disappeared without any

sequels at the time of the last interrogation.

Recovering/resolving: The intensity of signs and symptoms has been diminishing

and/or their clinical pattern has been changing up to the time of

the last interrogation in a way typical for its resolution.

Not recovered/not resolved: Signs and symptoms of an AE are mostly unchanged or

worsened at the time of the last interrogation.

Recovered/resolved with

sequel:

Actual signs and symptoms of an AE disappeared but there are

sequels related to the AE.

Fatal: Resulting in death. If there are more than one adverse event only

the adverse event leading to death will be characterized as 'fatal'.

Unknown The outcome is unknown or implausible and the information

cannot be supplemented or verified.

The action taken with the IMP will be assigned to one of the following categories:

Dose not changed: No change in the dose of the IMP.

Dose reduced: Reduction in the dose of the IMP.

Dose increased: Increase in the dose of the IMP.

Drug withdrawn: Discontinuation of the IMP.

Unknown: The information is unknown or implausible and it cannot be supplemented

or verified

Not applicable: The question is implausible (e.g. the subject is dead).

The term "countermeasures" refers to the specific actions taken to treat or alleviate adverse events or to avoid their sequels. Following categories will be used to categorize the countermeasures to adverse events:

None: No action taken.

Drug treatment: Newly-prescribed medication or change in dose of a medication.

Others: Other countermeasures, e.g. an operative procedure.

